Treatment Navigation for Opioid Use Disorders

Study Protocol

A113229 [name] (FA130694) (WA State Innovation Initiative- Medication Assisted Treatment upon Release from Prison)

[name], MSW, MPH	Principal Investigator	Alcohol and Drug Abuse Institute	[contact]
[name]	Co-Investigator	General Internal Medicine	
[name]	Co-Investigator	Psychiatry and Behavioral Sciences	[contact]
[name], RN	Co-Investigator	Health Services	[contact]
[name]	Project Director	Alcohol and Drug Abuse Institute	[contact]

Abstract

We will conduct a pilot randomized controlled trial (RCT) study. One hundred inmates with OUD releasing from WA State prisons to community corrections supervision in King County, WA will be enrolled (the county has a population of 2 million residents out of a state population of 7 million). Half of the subjects will receive treatment as usual, for instance outpatient drug counseling, and half will receive 6 months of intervention. The aims of this study are to determine: 1) whether study procedures can be implemented with fidelity, 2) whether offenders can be enrolled and maintained in the study, 3) which medications/treatment options subjects select and their experiences and satisfaction with the interventions, and 4) preliminary intervention effect size on outcomes of interest including recidivism, drug use, hospitalization, and treatment enrollment and retention.

Introduction

One-third of heroin users are incarcerated each year primarily due to criminal activity related to their drug use and *“policy changes and interventions are urgently needed to reduce the negative consequences of opioid relapse following re-entry”* (Fox et al., 2015). The number of heroin users and the number dying from opioid overdoses have increased significantly in recent years across the U.S. while pharmaceutical opioids remain a common pathway into heroin and a persistent overdose risk (Jones et al., 2015; Peavy et al., 2012).

The time shortly after release from prison is a period of greatly increased risk for fatal opioid overdose (Binswanger et al., 2013; Merrall et al., 2010). Opioid use disorder can be readily treated with medication assisted treatment (MAT) reducing criminal activity, recidivism, improving

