- 4) Unwilling to allow access to medical or drug treatment records, criminal history or criminal activity records.
- 5) Inability to communicate in English verbally.
- 6) Inability to provide adequate contact information to assist with follow-up.
- 7) Not planning on being in King County or reporting to community corrections in King County for 6 months.
- 8) Violent or overtly hostile/threatening towards research staff.
- 9) Entering 31 days or more controlled environment in the next 6 months.

Potential Subjects Identified

Recruitment, baseline interviews, and some follow-up interviews (if convenient for the subject) will take place in community corrections offices (CCOs) throughout King County. We will concentrate initially on offices in Seattle and South King County. Department of Corrections (DOC) will run weekly reports on inmates for upcoming releases to King County CCO facilities. DOC will notify CCO staff that a potential subject will be released to that facility. Once released, we will approach, recruit and enroll them during their first visit at the community corrections office and randomize to treatment as usual or intervention.

Obtain Informed Consent

Written informed consent will be obtained from all subjects who wish to participate in the study. Subjects will also be asked to complete HIPAA authorization agreements for treatment and medical records information and other secondary data sources.

Eligibility Screening

Subjects will be men or women aged 18-70 released from Washington State prisons to community corrections supervision in King county, meeting at least mild severity for Diagnostic and Statistical Manual of Mental Disorders Fifth Edition (DSM-5) criteria for diagnosis for opioid use disorder (e.g.

opiate dependence). Subjects will be asked to complete an eligibility screening questionnaire. The items covered are general demographics, proximity to the research settings, drug use questions, and DSM 5 checklist.

Baseline Assessments

Eligible subjects will undergo baseline assessments and provide information on personal information and health:

- 1) Opioid Use and Treatment Experiences: This assessment captures opioid use, overdose history, past treatment and feelings about future treatment.
- 2) Education, Employment, Income and Housing: This assessment captures other demographic information related to subject's resources and social stability.

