- 3) Overdose Risk Assessment: This assessment is used to determine the potential for future overdose based on prior overdose history, current drug use practices and social context for current drug use. This assessment is not standardized but is compiled from individual items of known risk factors for overdose.
- 4) World Health Organization Alcohol, Smoking and Substance Involvement Screening Test (WHO-ASSIST v.3). This is a multi-item tool to determine areas of substance use and misuse. This assessment battery screens for recent and lifetime use of a variety of substances, including illicit drugs, alcohol, pharmaceuticals and tobacco products.
- 5) EQ-5D-3L: This validated quality of life measure asks about problems in mobility, self-care, usual activities, pain and discomfort, anxiety and depression and overall health.

Locator information:

Subjects will be asked to provide a number of sources to ensure they can be contacted for follow-up visits. However, because we anticipate a number of subjects to have unstable housing, subjects may be enrolled if they provide at least one primary source of locator information.

Randomization

Subjects will be randomized to receive either standard of care or the study intervention. We will recruit equal numbers of subjects in the intervention and control arms of the study.

Follow-up Visits

Follow-up visits will occur at 1 and 6 months after enrollment. Interviews will be by phone or in-person. Assessments given at the baseline interview will be repeated at each follow-up point. In

addition to the assessments subjects will be asked questions in the intervention arm about how well the treatment navigation process is working.

Secondary Data Sources

Secondary data on health care and drug treatment utilization will be obtained from Washington State (separate IRB action pending) using the following sources:

- Division of Behavioral Health and Recovery (DBHR) data for drug treatment admissions data (formerly TARGET) and King County Behavioral Health and Recovery Division
- The Comprehensive Hospital Abstract Reporting System (CHARS) for hospital admissions
- Criminal History data extracted from Administrative Office of the Courts (AOC) and Department of Corrections (DOC) by the Washington Institute for Public Policy (WSIPP)
- Emergency Department Information Exchange data for emergency department visits administered by Collective Medical Technologies.

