regular reports for the 3-person data and safety monitoring oversight committee which will review any adverse events as well as monitor study progress to ensure that study results are scientifically valid.

The research coordinator for the study will conduct software programming and data management activities. Data will be stored on computer servers at ADAI that are fully HIPAA-compliant in accordance with the University of Washington School of Medicine. The senior computer specialist at ADAI maintains nightly tape backups and active disaster recovery protection and procedures. The research coordinator will develop data collection forms used by research staff. These forms will also have a companion data dictionary which comprehensively defines each data element. The data dictionary specifies missing, illogical, out of range, and inconsistent value checks for each data element, in addition to logic checks and assists the project data analysis.

Intervention fidelity monitoring

The primary threat to the integrity of the intervention is that the intervention may not be delivered as intended. This potential problem is minimized because the intervention is highly structured and intervention fidelity will be regularly monitored by co-investigators who will monitor audio recordings of intervention sessions after the interventionist has initially been approved to conduct interventions without supervision.

Data Analysis Plan

Analyses will allow us to evaluate the aims of this study: 1) whether study procedures can be implemented with fidelity, 2) whether offenders can be enrolled and maintained in the study, 3) which medications/treatment options subjects select and their experiences and satisfaction with the interventions and 4) preliminary intervention effect size on outcomes of interest including recidivism, drug use, hospitalization, and treatment enrollment and retention. The number of subjects is not intended to be adequate to test the impact of the intervention, but rather to provide sufficient numbers of subjects to assess the feasibility of both research study procedures and intervention components.

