The number and proportion of subjects retained at each step of the study will be documented and reported in a CONSRT diagram similar to the one in the Appendix for our current RCT. Baseline characteristics will be compared for each study arm to ensure randomization was properly implemented. Bi-variate test statistics of differences in outcomes of interest will be compared by study arm and reported for all outcomes. Study analyses will begin *prior* to study completion due to the fact that this is a pilot-feasibility trial and data will be used to determine if a full randomized trial is appropriate and what modifications to the study design are needed, this is different than procedures for a full RCT where analyses would await and complete, closed dataset. Data will be used to determine the possible treatment effect sizes which will allow sample size estimates to be calculated for a future full scale randomized controlled trial.

Equitable access to care and outcomes will be examined (Beletsky et al., 2015) by comparing the characteristics of the eligible pool of offenders with those screened, enrolled, and maintained throughout the study.

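### The pilot's effect sizes are meant to feed the full trial's sample size calculation, but the plan attaches no measure of precision to them; at 50 per arm the 95% half-width is about 0.39 SD

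*Combined protocol and SAP*

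**What the plan says.** The Abstract plans for "One hundred inmates with OUD releasing from WA State prisons", and the Randomization section adds "We will recruit equal numbers of subjects in the intervention and control arms of the study", so there are about 50 per arm. The fourth aim, given in the Abstract and again in the Data Analysis Plan, is a "preliminary intervention effect size on outcomes of interest including recidivism, drug use, hospitalization, and treatment enrollment and retention".

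For outcomes, the Data Analysis Plan states: "Bi-variate test statistics of differences in outcomes of interest will be compared by study arm and reported for all outcomes". It then gives two uses for the results. One is the decision on a next trial: "data will be used to determine if a full randomized trial is appropriate and what modifications to the study design are needed". The other is sizing that trial, for which the pilot should "determine the possible treatment effect sizes which will allow sample size estimates to be calculated for a future full scale randomized controlled trial".

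The same section limits what the sample is for: "The number of subjects is not intended to be adequate to test the impact of the intervention". The documents contain no interval, standard error or other precision measure for the effect sizes, and do not say how their uncertainty enters the later calculation.

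**The concern.** The effect size is the quantity that aim 4 hands to the next trial. A test statistic by arm does not show directly how large or small the true effect could be. Someone who takes the effect size forward without an interval may treat it as better known than it is.

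Two decisions could suffer: whether to run a full trial, and how large to make it. If a noisy estimate were used as though it were the truth, the full trial could be several times too small or too large. The statement that the sample is not meant to test the intervention does not cover this. It disclaims testing, and the same section still assigns the estimate to sizing.

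**Working it through.** **Inputs from the documents.** 100 subjects in equal arms, so 50 per arm (Abstract; Randomization). The documents give no confidence level, SD, event rate, effect or expected loss to follow-up. The 100 has no formula behind it, so there is no figure of the plan's own to reproduce.

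**Assumptions made here.** Two-sided 95% intervals; SD = 1 for continuous outcomes; 50 per arm with complete data, or 40 per arm followed; event rates of 5% vs 10%, 10% vs 20% and 25% vs 40%; a true effect of 0.3 SD; 80% power and two-sided 5% for the future trial.

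**Step 1: precision, continuous outcome.** SE = sqrt(2/n).
- 50 per arm: SE = sqrt(2/50) = 0.200; half-width = 1.96 × 0.200 = 0.392 SD.
- 40 per arm: SE = sqrt(2/40) = 0.224; half-width = 0.438 SD.
- An observed 0.3 SD at 50 per arm: 0.3 ± 0.392 = -0.09 to 0.69. A noncentral-t interval gives the same limits to within 0.005.

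**Step 2: precision, binary outcome.** Recidivism, hospitalization and treatment enrollment may well be analysed as proportions. Half-width = 1.96 × sqrt(p1(1-p1)/50 + p2(1-p2)/50).
- 5% vs 10%: 1.96 × sqrt(0.0475/50 + 0.09/50) = 0.103, about 10 points.
- 10% vs 20%: 1.96 × sqrt(0.09/50 + 0.16/50) = 0.139, about 14 points.
- 25% vs 40%: 1.96 × sqrt(0.1875/50 + 0.24/50) = 0.181, about 18 points.

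In each case the half-width exceeds the assumed difference (5, 10 and 15 points).

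**Step 3: sizing, only if the point estimate were the design effect.** Let the estimate be normal with mean 0.3 and SE 0.2, and let n per arm = 2 × ((1.960 + 0.842)/estimate)² for positive estimates.
- Correct n at 0.3 SD: 175 per arm.
- The 90th, 50th and 10th percentiles of the positive estimates are 0.564, 0.317 and 0.101, which give n = 49, 156 and 1,532.
- The next trial has under 50% true power when the estimate exceeds 0.429. The chance of that is 0.260; divided by the 0.933 chance of a positive estimate, this is 0.278, or about 28%.
- A further 6.7% of pilots would show no benefit, and no n could be calculated.

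For binary pilots simulated at 25% vs 40%, the 10th, 50th and 90th percentiles are 45, 136 and 963 per arm against a correct 152. Between 26% and 28% of those trials have under 50% power, depending on the formula.

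**Step 4: baseline adjustment.** The SE is multiplied by sqrt(1 - r²): 0.954 at r = 0.3 and 0.866 at r = 0.5, a cut of about 5% to 13%. At r = 0.5 the half-width is 0.392 × 0.866 = 0.34 SD, so this helps but does not solve the problem.

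**Step 5: a fixed target is not a guarantee.** A trial sized on 0.3 SD (175 per arm) has 80% power if the truth is 0.3 SD, 65% if it is 0.25 and 46% if it is 0.2.

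**The case against.** The strongest reply is that the plan never adopts point-estimate sizing. A reader might infer it from the sentence on sample size, but the wording does not support that. It speaks of effect sizes in the plural, calls them possible, and elsewhere calls them preliminary. A range of scenarios fits as well as a single plugged-in value. This stands, and Step 3 is therefore conditional.

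A second reply is that the pilot's limits are disclosed. This also stands. A reader might conclude that 100 subjects are too few, but the plan disclaims power to test the intervention and sets the number for feasibility. Low power in the pilot's own tests is not a fault.

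Third, the next trial's target difference belongs in that trial's protocol. That is right, and its absence here is not an error.

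Fourth, an interval can often be recovered from a t or z statistic and the arm sizes, or from arm counts for a binary outcome. This is partly true, but the plan does not commit to reporting what is needed for every outcome, and an interval is easier to read than to reconstruct.

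Finally, one might infer that any result at 50 per arm would be compatible with no effect. That goes too far: an observed 0.5 SD would have an interval of about 0.10 to 0.90, which excludes zero.

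**Conclusion.** The concern holds in a limited form. The plan uses the pilot's effect sizes for a later sample size calculation, reports test statistics by arm, and attaches no precision to the effects. The uncertainty is large: about ±0.39 SD at best and ±0.44 SD with 40 per arm followed, or about 10 to 18 percentage points at the assumed rates.

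The sizing consequence (about 50 to 1,530 per arm against a correct 175, with about 28% of trials under 50% true power) follows only if the point estimate alone became the design effect and the true effect were 0.3 SD. The documents neither state nor exclude the first condition, and the second is an assumption. The choice of 100 subjects and the three feasibility aims are not in question. The change should be made, but the pilot is sound without it for its feasibility purposes.

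**What to change.** In the Data Analysis Plan:

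1. Report each difference between arms with a 95% CI, and describe the test statistics as descriptive.
2. State that the pilot point estimate will not by itself set the full trial's size. The pilot would supply the control-arm rate, the SD and retention. Its CI would be used to check whether a target difference, justified on its own grounds, is plausible.
3. Where a matching baseline measure is already collected, also report a baseline-adjusted difference. For drug use, the Opioid Use and Treatment Experiences form ("This assessment captures opioid use, overdose history, past treatment and feelings about future treatment") and the WHO-ASSIST are both taken at baseline, and the Follow-up Visits section repeats the baseline assessments at 1 and 6 months. This part is minor.

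The cost is a few sentences and slightly more analysis, with no new data, visits or participants. The effect size will look less definite, someone will have to justify a target for the next trial, and that trial can still be underpowered if the true effect is smaller than the target.

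### The equity analysis uses an undefined eligible pool that overlaps the groups compared with it, so it can hide who was never reached and who was lost; compare continuers with non-continuers at each step

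*Combined protocol and SAP*

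**What the plan says.** The closing paragraph of the Data Analysis Plan describes the equity analysis in one sentence: "comparing the characteristics of the eligible pool of offenders with those screened, enrolled, and maintained throughout the study". It gives no definition of the pool, no list of characteristics, no statistical method, and no comparator made up of people who were not screened, not enrolled or lost.

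The recruitment path is set out under Potential Subjects Identified and Eligibility Screening. Before anyone is contacted, "Department of Corrections (DOC) will run weekly reports on inmates for upcoming releases to King County CCO facilities". After release, "we will approach, recruit and enroll them during their first visit at the community corrections office". Eligibility is then established from the person: "Subjects will be asked to complete an eligibility screening questionnaire", and "The items covered are general demographics, proximity to the research settings, drug use questions, and DSM 5 checklist". The Abstract sets the size: "One hundred inmates with OUD releasing from WA State prisons to community corrections supervision in King County, WA will be enrolled".

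Two other provisions bear on the point. The Data Analysis Plan will report how many subjects, and what proportion, remain at each step in a flow diagram; these are counts, not characteristics. The Data Safety Monitoring Oversight Committee section has the characteristics of subjects and of decliners reported to that committee.

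**The concern.** An equity analysis should show whether some kinds of people are reached, enrolled or kept less often than others. The natural contrast is between those who pass a step and those who do not. The plan instead holds up a reference group against people who largely belong to it. Such a contrast understates the gap by an amount that depends on how many continue, and it puts all earlier steps into the comparison with those maintained.

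The reference group is also not available as named. Several criteria, such as DSM-5 status, opioid use before incarceration and willingness to release records, need contact with the person or their answers. Nobody who was missed at the first office visit can be classified as eligible.

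At stake is the second aim, whether offenders can be enrolled and maintained, and the design changes for a full trial that the pilot is meant to inform. A small raw difference between pool and maintained could be taken as reassurance when a group is being lost.

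**Working it through.** **Inputs.** From the documents: 100 enrolled; DOC weekly reports as the only list that exists before screening; eligibility set by questionnaire. The documents give no pool size, retention rate, prevalence or test for this analysis, so there is no figure of the plan's own to reproduce. Everything numerical below except the 100 is an assumption: retention of 60-90%, pools of 125-1000, and a characteristic present in 40% of those who continue and 65% of those who do not (a 25-point gap), unless stated otherwise.

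**Step 1: what the pool can be.**
- *The DOC list.* It contains the screened, the enrolled and the maintained, so all three contrasts compare a whole with its part. It is also not a list of people known to be eligible.
- *Those found eligible at screening.* This is a subset of the screened, so nothing can be said about access to screening. It still contains the enrolled and the maintained, so those two contrasts still overlap.

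**Step 2: whole against part.** Let a fraction f continue, with prevalence S, and let the rest have prevalence C. The whole has W = fS + (1 - f)C, so

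W - S = (1 - f)(C - S),

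and the gap shrinks by a factor of 1/(1 - f). For loss after enrolment, f is retention:

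| Retention | Visible part of a 25-point gap | Shrinkage |
|---|---|---|
| 60% | 10 points | 2.5-fold |
| 67% | 8.3 points | 3-fold |
| 80% | 5 points | 5-fold |
| 90% | 2.5 points | 10-fold |

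**Step 3: the contrast the plan names.** Write P, E, M and L for the pool, enrolled, maintained and lost, and r for retention. Then

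P - M = (P - E) + (E - M), with E - M = (1 - r)(L - M).

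Loss after enrolment enters only through the shrunken second term, and the first term can offset it. Take P = 45%, M = 45%, L = 70% and r = 80%. Then E = 0.8 x 45 + 0.2 x 70 = 50%, and P - M = (45 - 50) + (50 - 45) = 0 points, although lost and kept differ by 25 points.

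**Step 4: the access steps.** Here f = 100/pool. The last two columns are simulated two-sided 5% tests of the 40% versus 65% gap.

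| Assumed pool | Shrinkage | Pool vs enrolled, treated as independent | Enrolled vs not enrolled |
|---|---|---|---|
| 125 | 5.0-fold | 0.0% reject | 64% |
| 150 | 3.0-fold | 6.7% | 85% |
| 200 | 2.0-fold | 57% | 95% |
| 400 | 1.33-fold | 97% | 99% |
| 1000 | 1.11-fold | 99.6% | 99.8% |

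With a large list little is lost. With a pool only slightly larger than the enrolled, which may happen if it means those found eligible at screening, much is lost.

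**Step 5: can pool versus maintained detect selective loss?** Take a pool of 400 at 45%, 100 enrolled also at 45%, 80 kept at 40% and 20 lost at 65%. The visible difference is 45 - 40 = 5 points. The calculation is approximate, using pq = 0.45 x 0.55 = 0.2475 throughout.
- Treated as independent: SE = sqrt(0.2475 x (1/400 + 1/80)) = 0.0609. The true SE, allowing for overlap, is sqrt(0.2475 x (1/80 - 1/400)) = 0.0497. The chance of rejecting is P(Z > (1.96 x 0.0609 - 0.05)/0.0497) = P(Z > 1.40), about 8%.
- Tested with the correct SE: P(Z > 1.96 - 0.05/0.0497) = P(Z > 0.95), about 17%.
- Kept versus lost directly: SE = sqrt(0.2475 x (1/80 + 1/20)) = 0.124, and P(Z > 1.96 - 0.25/0.124) is about 52%.

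**The case against.** The strongest reply is that the sentence is a description, not a test. Comparing participants with their source population answers a fair question: does the sample represent the pool? The bivariate tests in the Data Analysis Plan are attached to outcomes by arm, not to this comparison. The shrinkage is a fixed scale factor. If the variance allows for overlap, a whole-versus-part contrast has the same power as part versus remainder; with 100 enrolled and 80% kept, both simulate at 0.53. Step counts and decliner characteristics are planned as well.

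Much of this stands. Three stronger readings might be inferred, and the documents do not support them:
- *Each group is tested against its own subset.* The text sets every group against the pool; enrolled versus maintained is not a stated contrast, and no invalid test is specified.
- *Differences are diluted several-fold throughout.* That depends on a pool size and retention rate that are not given, and at the access steps it may be only 1.1- to 1.3-fold.
- *The trial would conclude that access was equitable.* There is no equity hypothesis, threshold or decision rule, equity is not among the four listed aims, and the plan says of its size that "The number of subjects is not intended to be adequate to test the impact of the intervention".

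What does not stand is the claim that nothing is lost. The equal-power result covers a part against everything outside it. For pool versus maintained, that remainder mixes people never enrolled with people lost later. Step 5 shows that even the correct variance then gives about 17% against 52%, and Step 3 shows that the signal can vanish. The flow diagram carries no characteristics, and the decliner data are planned for the committee rather than for this analysis.

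**Conclusion.** The point holds in a limited form. That the reference group is undefined, and that full eligibility is unknown for anyone not screened, follows from the text alone and rests on no assumed number. The shrinkage is an algebraic identity. Its size is conditional: 3- to 10-fold for loss after enrolment at an assumed 67-90% retention, and anywhere from slight to fivefold at enrolment across the assumed pools of 1000 down to 125. The cancellation example shows what is possible, not what is expected. The chance of missing selective loss rests on the assumed prevalences and on a test or an informal reading that the plan leaves open. For a descriptive analysis in a pilot the severity is modest; it is a free improvement rather than a flaw that threatens the trial's aims.

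**What to change.** Define the starting group as everyone on the DOC weekly release reports, using whichever characteristics are available for all of them, and stop calling it the eligible pool. At each step, compare those who continue with those who do not:
- approached and screened versus not;
- consented versus declined;
- enrolled versus eligible but not enrolled;
- followed versus lost, at 1 month and at 6 months.

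List the characteristics in advance and report each difference with a 95% confidence interval. The intervals will be wide. For 80 kept at 40% and 20 lost at 65%, the half-width is 1.96 x sqrt(0.40 x 0.60/80 + 0.65 x 0.35/20) = 23.5 points, so a 25-point gap would be reported as about 1.5 to 48.5. Absence of a clear difference should not be read as equity. The comparison with the source list may be kept, labelled as a description of representativeness.

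The cost is wording and analysis time. The data are largely planned already: DOC reports, screening answers, decliner characteristics, and baseline data on those later lost. The documents do not say which characteristics the DOC reports hold, so this should be confirmed before the first step is specified. No extra subjects or visits are needed.
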